## 1. Research Background and Rationale

Postoperative nausea and vomiting (PONV) is a common complication following surgery. Reports indicate that the incidence of PONV is 30% among all postoperative patients and can reach up to 80% in high-risk patients. Well-established risk factors for increased PONV include female sex, age under 50 years, non-smoking status, and a history of PONV or motion sickness [1, 2]. PONV not only diminishes patients' well-being, but may also result in severe consequences such as dehydration, electrolyte imbalance, wound dehiscence, and regurgitation with aspiration. These complications can lead to delayed recovery, unplanned hospital admission, and postponed return to work. Such outcomes are associated with prolonged recovery room stay, delayed discharge, and increased healthcare costs [3-5]. Procedures such as laparoscopy, gynecological surgery, and operations of longer duration are also associated with an increased incidence of PONV. Similarly, the use of general anesthesia and postoperative administration of opioid drugs contribute to a higher incidence of this complication [6, 7].

It is well established that conventional opioid drugs increase the risk of PONV in a dose-dependent manner [8]. Although the exact mechanisms by which opioid drugs cause nausea and vomiting are not yet fully understood, multiple mechanisms may be involved [9]. At the cellular level, traditional opioid agonists bind to the MOR and stimulate G protein signaling to produce analgesia, while activation of the  $\beta$ -arrestin pathway leads to adverse effects related to respiratory and gastrointestinal function [10]. In preclinical studies,  $\beta$ -arrestin-2 gene knockout mice treated with morphine exhibited enhanced analgesic effects and reduced respiratory depression and gastrointestinal dysfunction compared with wild-type animals treated with morphine [11, 12].

Oliceridine is a new generation intravenous opioid drug and a G protein-selective agonist. Oliceridine was approved for marketing in China in May 2023. In two randomized, double-blind, placebo- and morphine-controlled phase 3 pivotal studies, oliceridine provided rapid and effective analgesia with a favorable safety profile [13, 14]. In these two studies, the incidence of nausea in the 0.1 mg (40%) and 0.35 mg (59%) demand dose groups was lower than that in the morphine 1 mg group (70%), with the relative risk in the 0.1 mg demand dose group being 43% ( $P<0.001$ ). The incidence of vomiting for oliceridine at three different required doses—0.1 mg (20%),

0.35 mg (30%), and 0.5 mg (42%)—was lower than that reported for morphine 1 mg (52%), with the relative risk for the 0.1 mg and 0.5 mg doses significantly reduced by 41%–61% ( $P < 0.001$ ) [15, 16]. Hammer et al. [23] performed an exploratory analysis of these two trial datasets, defining the absence of vomiting and the non-use of rescue antiemetic medications as 'complete gastrointestinal response' as a composite endpoint. The analysis demonstrated that, compared to morphine, oliceridine achieved a 2–3-fold higher rate of 'complete gastrointestinal response' [16].

Gynecological surgical procedures predominantly involve the pelvic and abdominal cavities. Intraoperative mechanical traction and compression of pelvic and abdominal organs readily stimulate the vagus nerve and visceral afferent nerves, resulting in the release of central neurotransmitters that trigger PONV. It is noteworthy that with the widespread adoption of gynecological laparoscopic surgery, intraoperative pneumoperitoneum and the Trendelenburg position can increase intra-abdominal pressure, stimulating gastrointestinal emetic receptors and inducing PONV [17].

Oliceridine demonstrates safe and effective analgesic properties, with a marked advantage in gastrointestinal tolerability, which may support its rational application in gynecological surgery. This also constitutes the rationale for our research. However, oliceridine has only recently been introduced to the market, and there remains a lack of robust clinical evidence regarding its use in general anesthesia. Therefore, this study is designed as a randomized controlled trial, using sufentanil—a commonly used opioid drug in clinical practice—as the control, to compare the incidence of postoperative nausea and vomiting (PONV) following gynecological laparoscopic surgery.

## **2. Research Objectives**

To explore the effects of oliceridine versus sufentanil on postoperative nausea and vomiting after gynecological laparoscopic surgery.

## **3. Research Protocol and Plan**

### **3.1 Study Design**

This study is a randomized, double-blind, parallel-controlled clinical trial to be conducted in the Department of Anesthesiology at the Second Xiangya Hospital of Central South University. Prior to initiation, the study will be approved by the hospital's medical ethics committee, and informed consent will be obtained from patients or their families. Patients will be randomized according to a computer-

generated randomization sequence into the sufentanil group and the oliceridine group. The sufentanil group will receive sufentanil for both anesthesia and postoperative analgesia, while the oliceridine group will receive oliceridine for both anesthesia and postoperative analgesia. Group allocation results are delivered to the anesthesia nurse using the sealed envelope method. Based on the study design and allocation, injection solutions with identical appearance and volume are prepared and provided to the attending anesthesiologist. The anesthesia nurse responsible for drug preparation does not participate in patient recruitment, randomization, data collection, or analysis.

### 3.2 Study Population

Inclusion criteria: Elective gynecological laparoscopic surgery; age 18–65 years; American Society of Anesthesiologists (ASA) physical status I–III; and body mass index (BMI) 18–30 kg/m^2.

Exclusion criteria: Severe dysfunction of major organs such as the heart, lungs, or brain; history of allergy to opioid drugs, propofol, soybeans, or eggs; recent use of sedatives, analgesics, or monoamine oxidase inhibitors; history of alcohol abuse; obstructive sleep apnea syndrome; difficult airway; psychiatric or neurological disorders; communication disorders; or women who are lactating or pregnant.

Withdrawal criteria: Subject requests withdrawal or withdraws voluntarily; change in surgical method requiring combined gastrointestinal surgery; occurrence of allergy to the investigational drug or life-threatening complications; or reoperation within 48 hours postoperatively due to bleeding or other factors.

### 3.3 Group Allocation and Interventions

Patients were randomly assigned to either the Sufentanil group or the Oliceridine group. No preoperative medications were administered. Upon entering the operating room, standard monitoring of ECG, SpO2, BP, and BIS was implemented, and intravenous access was established. Anesthesia induction: Sequential intravenous administration of midazolam 0.05–0.10 mg/kg, sufentanil 0.3 µg/kg (Sufentanil group) or oliceridine (0.06 mg/kg, based on the oliceridine injection package insert, where 1 mg oliceridine is approximately equivalent to 5 mg morphine), and propofol 1.5~2.0 mg/kg and cisatracurium besylate 0.2~0.3 mg/kg. Following intubation, both groups of patients underwent volume-controlled mechanical ventilation, with a tidal volume of 6~8 ml/kg, respiratory rate of 8~12 breaths/min, and an inspiratory-to-expiratory ratio of 1:2. Ventilation parameters were adjusted to maintain PCO2 at 35~40 mmHg (1 mmHg = 0.133 kPa). Prior to skin incision, patients received sufentanil 0.1–0.2

μg/kg (Sufentanil group) or oliceridine 0.02–0.04 mg/kg (Oliceridine group). Total intravenous anesthesia was maintained intraoperatively with continuous infusion of propofol at 4–10 mg/kg/h and remifentanil at 0.1–0.2 μg/kg/min, along with intermittent intravenous injections of cisatracurium besylate 4 mg. Approximately 30 minutes before the end of surgery, sufentanil 0.1 μg/kg (Sufentanil group) or oliceridine 0.02 mg/kg (Oliceridine group) was administered.

Postoperative analgesia protocol: The Sufentanil group received 2 μg/kg sufentanil, and the Oliceridine group received 0.4 mg/kg oliceridine. Ondansetron 8 mg and dexamethasone 10 mg were added to normal saline to a total volume of 100 ml. The initial loading dose was 2 ml, with no background infusion. Each bolus dose was 2 ml, the lockout interval was 10 minutes, and the maximum dose was 10 ml/h. All enrolled patients were connected to the electronic analgesia pump immediately after surgery, and patients and their families received preoperative instruction on the use of the electronic analgesia pump. If postoperative pain could not be alleviated by the analgesia pump, the anesthesiologist administered rescue sufentanil 5 μg or oliceridine 0.2 mg as needed. If rescue therapy is ineffective, the anesthesiologist will determine alternative remedial measures and document the medications and dosages administered. If the patient develops PONV of grade 2 or above, a combination of ondansetron 4 mg and dexamethasone 5 mg will be administered intravenously. If symptoms are not alleviated after one hour, haloperidol 1 mg will be administered in combination.

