Postoperative analgesia assessment: Resting visual analog scale (VAS) pain scores at four time points (T1–T4) within 48 hours after surgery, measured using a 10 cm movable ruler with a numerical scale of 0–10 on the reverse side. The left end (“0”) indicates no pain, while the right end (“10”) represents unbearable severe pain. Record the number of PCA presses, total analgesic consumption, and the use of rescue analgesics within 48 hours after surgery.

Ramsay sedation score at 2 hours postoperatively: a score of 1 indicates agitation, 3 or 4 indicates somnolence, and 5 or 6 indicates excessive sedation.

Sleep quality score on the night after surgery: Patient sleep quality will be assessed using a numerical rating scale based on an 11-point Likert scale, ranging from 0 to 10. A score of 0 indicates complete insomnia and extremely poor sleep quality, while a score of 10 represents excellent sleep quality. Severe insomnia is defined as a score of 0–3, moderate insomnia as 4–6, and good sleep quality as 7–10.

QOR-15 score: A score of 0 indicates extremely poor quality of recovery, while a score of 150 indicates excellent quality of recovery. Assessments will be conducted preoperatively, on postoperative day 1, and on postoperative day 3.

Length of stay in the recovery room, time to first postoperative bowel movement, time to resumption of oral intake, time to first postoperative feeding, time to first

postoperative ambulation, and any other adverse events.

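### The rescue opioid doses (5 micrograms sufentanil or 0.2 mg oliceridine) depart five-fold, without explanation, from the ratio implied by the four other paired doses

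*Combined protocol and SAP*

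**What the plan says.** Section 3.3 (Group Allocation and Interventions) gives the study opioid at five points, each as a sufentanil dose and a counterpart oliceridine dose:

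- induction: 0.3 micrograms/kg or 0.06 mg/kg;
- before incision: 0.1–0.2 micrograms/kg or 0.02–0.04 mg/kg;
- about half an hour before the end of surgery: 0.1 micrograms/kg or 0.02 mg/kg;
- patient-controlled pump, made up to 100 ml: sufentanil 2 micrograms/kg, while "the Oliceridine group received 0.4 mg/kg oliceridine". The loading dose and each bolus are 2 ml;
- rescue: "If postoperative pain could not be alleviated by the analgesia pump, the anesthesiologist administered rescue sufentanil 5" micrograms "or oliceridine 0.2 mg as needed".

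If rescue fails, "the anesthesiologist will determine alternative remedial measures and document the medications and dosages administered".

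The only potency relation in the document is attached to the induction dose: "where 1 mg oliceridine is approximately equivalent to 5 mg morphine". No sufentanil-to-oliceridine conversion is stated, and no reason is given for the rescue doses.

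Section 3.4 lists the related data: "Record the number of PCA presses, total analgesic consumption, and the use of rescue analgesics within 48 hours after surgery". Section 3.1 says that "injection solutions with identical appearance and volume are prepared and provided to the attending anesthesiologist", without saying whether this includes rescue doses.

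**The concern.** Four dosing points share one ratio and the fifth does not. The odd one out is the dose meant for patients whose pain the pump has not controlled.

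This matters because the opioid is the randomised treatment. Section 1 states that "conventional opioid drugs increase the risk of PONV in a dose-dependent manner", and the primary outcome is PONV within 48 hours. If rescue delivers relatively more opioid in the sufentanil arm, part of a PONV difference in favour of oliceridine could come from the rescue rule and not from the drug. The VAS pain scores, rescue use and analgesic consumption are exposed more directly. A reader could use the imbalance to question a favourable result.

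**Working it through.** **Step 1: the ratio at each point.** All doses are from Section 3.3. Ratio = sufentanil dose (micrograms or micrograms/kg) ÷ oliceridine dose (mg or mg/kg).

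| Dosing point | Calculation | Micrograms per mg |
|---|---|---|
| Induction | 0.3 / 0.06 | 5 |
| Pre-incision, lower end | 0.1 / 0.02 | 5 |
| Pre-incision, upper end | 0.2 / 0.04 | 5 |
| End of surgery | 0.1 / 0.02 | 5 |
| Pump | 2 / 0.4 | 5 |
| Rescue | 5 / 0.2 | 25 |

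The departure is 25 / 5 = 5-fold. Weight cancels within each pair, so fixed and per-kg pairs can be compared. Crossing the ends of the pre-incision ranges gives 0.1/0.04 = 2.5 to 0.2/0.02 = 10, which does not reach 25.

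**Step 2: rescue against one pump press.** A press is 2 of 100 ml, so 0.04 micrograms/kg sufentanil or 0.008 mg/kg oliceridine. At an assumed 60 kg this is 2.4 micrograms or 0.48 mg.

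- Sufentanil rescue: 5 / 2.4 = 2.08 presses.
- Oliceridine rescue: 0.2 / 0.48 = 0.42 of a press.

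**Step 3: effect on one patient's exposure.** For bookkeeping only, both arms are put on the implied 5:1 scale, in sufentanil micrograms. This is not a claim of equal analgesia. One rescue counts 5 in the sufentanil arm and 0.2 × 5 = 1 in the oliceridine arm. Assume 60 kg, the loading dose plus 10 boluses (11 × 2.4 = 26.4) and *r* rescues in each arm. The postoperative ratio is (26.4 + 5*r*) / (26.4 + *r*). Intraoperative study opioid, taking the middle of the pre-incision range and leaving out remifentanil, adds (0.3 + 0.15 + 0.1) × 60 = 33 to both arms.

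| Rescues per arm | Postoperative | With intraoperative |
|---|---|---|
| 1 | 31.4 / 27.4 = 1.15 | 64.4 / 60.4 = 1.07 |
| 3 | 41.4 / 29.4 = 1.41 | 74.4 / 62.4 = 1.19 |
| 5 | 51.4 / 31.4 = 1.64 | 84.4 / 64.4 = 1.31 |

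Over 45–75 kg and 5–30 boluses, the postoperative ratio runs:

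- 1 rescue: from 98/94 = 1.04 to 15.8/11.8 = 1.34;
- 3 rescues: from 108/96 = 1.13 to 25.8/13.8 = 1.87;
- 5 rescues: from 118/98 = 1.20 to 35.8/15.8 = 2.27.

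The low end is 75 kg with 30 boluses (31 × 3.0 = 93). The high end is 45 kg with 5 boluses (6 × 1.8 = 10.8).

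**Step 4: effect on the arm mean.** If a fraction *f* of each arm has one rescue (60 kg, 10 boluses), the postoperative ratio is (26.4 + 5*f*) / (26.4 + *f*):

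- *f* = 0.1: 26.9 / 26.5 = 1.02
- *f* = 0.3: 27.9 / 26.7 = 1.04
- *f* = 0.5: 28.9 / 26.9 = 1.07

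**Step 5: what would cancel the gap.** One rescue leaves a gap of 5 − 1 = 4 micrograms on this scale. Five oliceridine rescues per sufentanil rescue close it (31.4 / 31.4 = 1.00), and six reverse it (31.4 / 32.4 = 0.97). Extra oliceridine presses also close it: 4 / (0.04 × weight) = 2.2, 1.7 and 1.3 presses at 45, 60 and 75 kg.

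Weights, bolus counts and rescue counts are assumptions; the documents give none of them.

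**The case against.** The strongest reply is that nothing has been miscalculated. The protocol states no sufentanil–oliceridine conversion, so 5:1 is the reader's inference, and nothing obliges an as-needed rescue dose to follow the ratio of the scheduled doses. That is fair as to the label: this is an unexplained inconsistency between dosing points, not a wrong sum. But four exact agreements, including the pump that rescue supplements, are a pattern that a five-fold exception should explain. Fixed dosing at rescue does not explain it, because weight cancels.

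The second reply is that the consequence is small and may correct itself. Arm-mean ratios are at most 1.07 in the single-rescue cases above, and both arms also receive remifentanil. Patients control the pump, and fewer than two extra presses at 60 kg offset one rescue. This stands as a limit on the size of the effect. Compensation cannot be relied on, though, since rescue is reserved for patients in whom the pump has not been enough. The largest ratios, up to 2.27, need low weight, few presses and five rescues. That is an unlikely combination and should carry no weight.

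Third, rescue is part of each assigned regimen, so the randomised comparison of the regimens as written remains valid. That is correct. What suffers is the reading of the result as a difference between the drugs.

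Finally, a breach of the blind is not shown, because the identical preparation in Section 3.1 may cover rescue doses.

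**Conclusion.** The concern holds. On the scale implied by every other dosing point, the rescue pair is unequal by a factor of five per dose at any body weight, and the document does not say why. Confidence in that ratio is high.

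The effect on outcomes is much less certain. Total exposure shifts far less than five-fold, and its size depends on assumed weights and on pump and rescue use. The effect on PONV cannot be computed, because the plan gives neither a rescue frequency nor a dose–response slope. The imbalance could favour oliceridine on the primary outcome, but repeat rescue, extra presses or other remedies in that arm could cancel or reverse it. The point should be fixed, because the dosing text is inconsistent as written and correcting it is cheap.

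**What to change.** Reconcile the rescue pair in Section 3.3 with the ratio at the other four dosing points, or state the rationale for a different one. The choice of dose belongs to the clinical team, and none is proposed here. This is a one-line change and needs no more patients. The documents do not give enrolment status; if enrolment has begun, the change needs a protocol amendment, and rescue use should be shown before and after it.

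Two optional additions would help:

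- one sentence saying whether the identical preparation in Section 3.1 covers rescue doses;
- one by-arm table beside the primary result with patients rescued, number of doses, and drug and amount, including alternative measures. Sections 3.3 and 3.4 already call for these data. If both opioids are put on a common scale, define that scale in advance.

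### The rescue opioid pair (sufentanil 5 µg or oliceridine 0.2 mg) departs fivefold, without explanation, from the ratio used for every other dose pair

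*Combined protocol and SAP*

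**What the plan says.** Section 3.3 gives three scheduled opioid doses during anesthesia, each as a sufentanil–oliceridine pair per kilogram. For the pump, sufentanil patients have 2 µg/kg and "the Oliceridine group received 0.4 mg/kg oliceridine", made up to 100 ml. The settings are the same in both arms: "Each bolus dose was 2 ml, the lockout interval was 10 minutes, and the maximum dose was 10 ml/h".

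When the pump does not control pain, the anesthesiologist gives a fixed rescue of sufentanil 5 µg or "oliceridine 0.2 mg as needed". The next step is also specified: "If rescue therapy is ineffective, the anesthesiologist will determine alternative remedial measures and document the medications and dosages administered".

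The only equivalence that the protocol states is between oliceridine and morphine, at induction: "where 1 mg oliceridine is approximately equivalent to 5 mg morphine". It states no sufentanil–oliceridine conversion.

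Among the secondary outcomes, Section 3.4 lists resting VAS at T1–T4 and this instruction: "Record the number of PCA presses, total analgesic consumption, and the use of rescue analgesics within 48 hours" after surgery.

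**The concern.** Four dose pairs share one ratio and the fifth does not, with nothing in the text to explain the change. The odd one out is the dose for patients whose pump has already proved insufficient. Followed as written, an oliceridine patient then receives less drug than one further press would deliver, while a sufentanil patient receives more than one press.

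At stake is the reading of the secondary analgesia outcomes. From the first rescue onward, the arms differ both in drug and in the relative size of the rescue. More repeat rescues, more escalation, more pump presses or higher pain scores with oliceridine could come from the smaller dose. Randomization does not remove a difference that the protocol itself prescribes.

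**Working it through.** **Step 1: dose ratios.** All inputs are from Section 3.3. The ratio is µg sufentanil divided by mg oliceridine.

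| Step | Sufentanil | Oliceridine | µg per mg |
|---|---|---|---|
| Induction | 0.3 µg/kg | 0.06 mg/kg | 0.3/0.06 = 5 |
| Before incision | 0.1–0.2 µg/kg | 0.02–0.04 mg/kg | 0.1/0.02 = 0.2/0.04 = 5 |
| About 30 min before end | 0.1 µg/kg | 0.02 mg/kg | 0.1/0.02 = 5 |
| PCA reservoir | 2 µg/kg | 0.4 mg/kg | 2/0.4 = 5 |
| Rescue | 5 µg | 0.2 mg | 5/0.2 = **25** |

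By mass, oliceridine to sufentanil is 200:1 for the first four pairs and 40:1 for rescue. The protocol states no such ratio, so there is no printed figure to reproduce; 5 µg per mg is inferred from its own pairs.

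**Step 2: one pump bolus at weight w kg.** The reservoir is 100 ml and the bolus 2 ml.
- Sufentanil: 2w/100 × 2 = 0.04w µg.
- Oliceridine: 0.4w/100 × 2 = 0.008w mg.

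**Step 3: one rescue expressed in the same arm's boluses.** This step needs no equivalence between the drugs.
- Sufentanil: 5/(0.04w) = 125/w.
- Oliceridine: 0.2/(0.008w) = 25/w.

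The quotient is 125/25 = 5 at every weight. The documents give no body weights, so the weights below are assumptions: 60 kg as an example, and the span from 18 × 1.50² = 40.5 kg to 30 × 1.75² = 91.9 kg (the eligible BMI limits at assumed heights of 1.50 and 1.75 m).

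| Weight | Sufentanil rescue, boluses | Oliceridine rescue, boluses |
|---|---|---|
| 40.5 kg | 3.09 | 0.62 |
| 60 kg | 5/2.4 = 2.08 | 0.2/0.48 = 0.42 |
| 91.9 kg | 1.36 | 0.27 |

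**Step 4: does the direction hold for all eligible patients?** The sufentanil rescue exceeds one bolus when w < 125 kg. The oliceridine rescue is below one bolus when w > 25 kg. Section 3.2 requires "body mass index (BMI) 18–30 kg/m"². Reaching 125 kg at BMI 30 needs a height of √(125/30) = 2.04 m. Falling to 25 kg at BMI 18 needs √(25/18) = 1.18 m. In practice every eligible adult lies between these limits.

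**Step 5: share of the hourly pump maximum at 60 kg.** Ten ml is 5 × 2.4 = 12 µg or 5 × 0.48 = 2.4 mg. One rescue is 5/12 = 42% of that maximum with sufentanil and 0.2/2.4 = 8% with oliceridine.

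**Step 6: the matched dose.** At 5 µg per mg, the partner of sufentanil 5 µg is oliceridine 5/5 = 1.0 mg, which at 60 kg is 1.0/0.48 = 2.08 boluses, the same as in the sufentanil arm. The written 0.2 mg is one fifth of that.

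**The case against.** The best defence has three parts.

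- **Rescue adds to the pump.** It does not replace a press, it is given as needed with no stated limit on repeats, and a failed rescue leads to further measures that are recorded. This stands as mitigation. A reader might infer that oliceridine patients are left without adequate relief; the documents do not support that. The imbalance remains all the same: reaching the same relative dose takes five oliceridine rescues for one of sufentanil, and repeats and escalation are themselves ways in which the written dose would show in the results.
- **0.2 mg may be intended.** It lies within the 0.1–0.5 mg demand doses cited in Section 1, so a deliberate low dose is possible. Against that, the protocol's own bolus is 0.48 mg at 60 kg and can be repeated every 10 minutes up to the hourly maximum. The documents do not settle the matter, and reading 0.2 mg as a slip for 1 mg would also go beyond them.
- **5 µg per mg is only inferred.** True, but the comparison with each arm's own pump does not rely on it.

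A further tempting reading is that the relatively larger sufentanil rescue biases PONV in favour of oliceridine, since Section 1 says that opioids raise PONV risk with dose. This cannot be shown. The documents give no rescue rate, no number of rescues per patient and no expected PCA volume. A smaller oliceridine rescue could also lead to more repeats, more pump use or other drugs, so the direction of any net effect is open too.

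**Conclusion.** The point holds as an unexplained inconsistency in one dose pair: 25 against 5 µg per mg, a fivefold difference relative to each arm's pump at any weight. The figure of 2.08 versus 0.42 boluses assumes 60 kg; the direction needs only the BMI limits and ordinary adult height.

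The proportion needing a first rescue is unaffected. It would be too generous to say the same of PCA presses and consumption: both are collected over 48 hours, the pump stays available after a rescue, and a patient with a weaker rescue may press more. Those measures, repeat rescues, escalation, VAS after a rescue and any total that includes rescue are open to the dose difference. How far depends on how many patients are rescued, which the documents do not say.

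The plan should be changed, but the point does not show that the primary comparison is invalid. No size is claimed for the effect on total opioid or PONV.

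**What to change.** 1. Check 0.2 mg against the package insert, whose dose limits the protocol does not reproduce. Then correct the pair to the protocol's own 5 µg : 1 mg ratio: oliceridine 1 mg against sufentanil 5 µg. If single-dose limits require less, lower both doses at the same ratio.
2. If 0.2 mg is deliberate, give the reason in Section 3.3 and treat repeat-rescue counts and post-rescue analgesia outcomes as descriptive.
3. In Section 3.4, state whether total analgesic consumption includes rescue, and in what unit. Presses and rescue use are already separate items, so little else needs to change there.

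The cost is a short amendment to one dose pair and one outcome definition. The clinical downside is a larger single oliceridine dose on top of PCA, which needs the usual observation after an opioid. One mg is also twice the highest demand dose cited in Section 1 (1.0/0.5 = 2). That demand dose is not a stated safety limit, but it is a reason to do the package-insert check first. Lowering both doses instead would weaken the sufentanil rescue, so that route should be taken only if the limits require it.
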